The study treatment duration will be two years. All subjects who complete or discontinue from the study, for any reason, will have a follow-up visit four weeks after the end of treatment visit. Subjects who complete the study will have a liver biopsy performed at M24. Subjects who discontinue the study prematurely will be contacted and asked to sign a separate consent to return for a Month 24 liver biopsy (primary endpoint).

Schema:

*A biopsy must be conducted if previous biopsy (bx) was >3 months prior to Day 1 or if tissue is not available.

Title: A Multicenter, Double-Blind, Randomized Trial of IDN-6556 in Subjects Who had Hepatitis C Virus (HCV) Reinfection and Liver Fibrosis or Cirrhosis following Orthotopic Liver Transplantation for Chronic HCV Infection and Who Subsequently Achieved a Sustained Virologic Response Following anti-HCV Therapy

Dosage and Administration:

IDN-6556 will be double-blind with matching placebo. 25 mg of IDN-6556 or placebo will be administered orally twice a day, preferably with food.

Drug Supply:

IDN-6556 will be supplied in bottles containing 60 capsules, each containing 25 mg of IDN-6556. Matching placebo will be supplied in bottles containing 60 capsules.

Subject Entry Criteria (Refer to protocol **Sections 7.1 and 7.2** for full entry criteria)

Key Inclusion Criteria:

1. Male or female subjects of minimum adult legal age (according to local laws for signing the informed consent document), able to provide written informed consent, and able to understand and willing to comply with the requirements of the study
2. History of orthotopic liver transplantation for HCV-induced liver disease
Note: Living donor or cadaveric transplantation will be permitted into the study. HCV positive donor livers will also be permitted into the study.
3. Diagnosis of HCV infection (HCV-RNA detectable in serum) and liver fibrosis or cirrhosis status post liver transplantation, and achieved a sustained virologic response (SVR) with anti-viral HCV treatment within 18 months of Day 1
Note: For the purposes of this study, subjects must meet the definition of SVR as defined by the anti-HCV regimen used.
4. Liver fibrosis or cirrhosis on liver histology as read by central histopathologist of Ishak F2 to F6 within three months of Day 1
Note: Baseline liver histology in close approximation of the three month window may be permitted on a case by case basis after discussion with the Medical Monitor.

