4 PLANNED SIZE DETERMINATION

This study will be conducted at multiple centers at which approximately 60 subjects will be enrolled and treated in a 2:1 ratio with emricasan or placebo, respectively. The sample size determination for this study is based on the Phase 2b screening methodology presented in [Fleming and Richardson \(2004\)](#).

The base case for the placebo response rate of 30% was assumed and obtained from [George, et al \(2009\)](#), where it stated that 29% of patients showed a response in fibrosis from a mean of 1.6 years following HCV-SVR.

Treatment duration for all subjects is expected to be two years. The primary analysis of this Phase 2 “screening” study is formally based on a three-category decision guideline. The decision guideline for this study is based on whether the difference in the proportions of subjects who show a response (i.e., improvement or no change) per their Ishak Fibrosis Score at 24 months for emricasan compared to placebo is less than 5%, is from 5% up to 15%, or is more than 15%. Specifically, the outcome of the study will determine one of the following three course of action:

1. If the difference in response rates between emricasan and placebo (i.e., emricasan response rate – placebo response rate) is less than 5%, then emricasan regimen is not plausibly more efficacious than placebo; hence, emricasan or its utility in this indication will be reconsidered.
2. If the difference in response rates between emricasan and placebo is from 5% up to 15%, then emricasan is plausibly more efficacious than placebo in this indication if secondary analyses of biomarkers suggest utility of emricasan or a positive safety profile is observed; hence, emricasan could be evaluated in a subsequent Phase 3 clinical study.
3. If the difference in response rates between emricasan and placebo is more than 15%, then emricasan could be evaluated in a subsequent Phase 3 study.

These categories should not be interpreted as providing strict decision rules but rather as guidelines that will be factored into a broader scientific assessment of the benefit to risk profile for emricasan in this indication. This broader assessment will include consideration of secondary efficacy analyses, safety profile, and relevant information external to this study.

The operating characteristics for this three-category decision guideline are shown in Table 1.

Table 1. Operating Characteristics for Three-Category Decision Guideline

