Probability of Obtaining an Estimated Treatment Effect (Emricasan – Placebo)			
True Treatment Effect (TE)	≤5%	5%≤ TE <15%	≥15%
0	67%	22%	11%
5	52%	26%	22%
10	36%	27%	37%
15	23%	24%	53%
20	13%	19%	68%
25	7%	13%	80%
30	3%	8%	89%

Note: Based on 100,000 simulations.

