9.1 PRIMARY EFFICACY ANALYSIS

All screening and post-baseline biopsy data collected will be used in the primary analysis, irrespective of the defined protocol visit window. Classification of the Ishak fibrosis score will be summarized descriptively by treatment group at baseline, Month 12, and Month 24. Response at Months 12 and 24 will be summarized descriptively by treatment group, along with exact (Clopper-Pearson) 95% confidence intervals (CIs). The risk difference between groups will also be provided with its 95% CI.

For the primary efficacy analysis based on the Month 24 biopsy, subjects with a missing Month 24 biopsy will have their Ishak fibrosis score imputed. Imputation of missing Ishak fibrosis scores will be conducted using multiple imputation (MI). Results will be imputed based on age, gender, baseline Ishak fibrosis score, and the Month 12 Ishak fibrosis score. Imputations will be based on at least 5 imputed datasets, depending on the percent of missing observations and will be documented in the clinical study report. Within each imputed dataset, the change from baseline at Month 24 will be derived to allow categorization into response or no response as defined in [Section 5.1](#).

Study success will be determined per the criteria described in [Section 0](#). This primary analysis will be conducted using the FAS.

The following sensitivity analyses will be provided for the primary efficacy endpoint, using different methods for the handling of missing liver biopsy results at Month 24:

- All FAS observed post-baseline biopsies
- All FAS observed post-baseline at Month 24 (within the sensitivity analysis visit window, per [Section 3.5](#))
- FAS with missing M24 biopsy imputed to ‘No’ response
- Per-protocol

Response rates at Month 12 will be summarized using the FAS in the same manner as the response rates at Month 24 (i.e., using MI). Subjects with a missing Month 12 liver biopsy will have their Month 12 Ishak fibrosis score imputed based on age, gender, and baseline Ishak fibrosis score.

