12 HANDLING OF MISSING DATA

The details of handling missing data for the primary endpoint are provided in [Section 9.1](#). There will be no imputations made for any of the secondary endpoints.

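### Both imputation models in SAP 9.1 leave out randomised arm, so a real emricasan–placebo difference is pulled toward zero before it is read against the 5%/15% guideline

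*SAP*

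**What the plan says.** SAP 9.1 bases the primary analysis on the Month 24 biopsy in the Full Analysis Set and imputes the Ishak score where that biopsy is missing. The predictors are given as a closed list: "Results will be imputed based on age, gender, baseline Ishak fibrosis score, and the Month 12 Ishak fibrosis score". For the Month 12 summary, subjects without that biopsy "will have their Month 12 Ishak fibrosis score imputed based on age, gender, and baseline Ishak fibrosis score". Neither list contains treatment group. The same section does say that the descriptive summaries are by treatment group, but says nothing similar about the imputation.

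No other section supplies the missing term. Protocol 12.6.5 leaves missing-data methods to the SAP. SAP 12 refers back: "The details of handling missing data for the primary endpoint are provided in" Section 9.1. SAP 14 lists no change to the imputation variables. How a subject lacking both biopsies is handled is not stated.

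The imputed result is the one that counts. SAP 9.1 continues: "Study success will be determined per the criteria described in" a section whose number prints as 0. The only such criteria are in SAP Section 4, where the difference in response rates falls below 5%, between 5% and 15%, or above 15%.

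**The concern.** The analysis compares arms, while the imputation assumes that arm makes no difference once age, sex, baseline score and Month 12 score are known. An imputed emricasan subject and an imputed placebo subject with the same values get draws from the same distribution. An observed Month 12 score passes on only the part of the drug effect already visible at that biopsy. A Month 12 score filled by its own arm-free model passes on none.

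At stake is the main reading of the trial. If the drug works and biopsies are missing at random within arm, the primary estimate is too small, and an effective drug reaches the top category less often than SAP Table 1 indicates. SAP 9.2.1 applies its stratified tests to each analysis in 9.1, so the main test appears to use the same imputed data.

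**Working it through.** **Inputs from the documents.** 40 emricasan and 20 placebo subjects (SAP 3.3); placebo response 30% (SAP 4); thresholds 5% and 15% (SAP 4); at least 5 imputations (SAP 9.1).

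**Assumptions.** The missing Month 24 rate is not given, so 10, 20 and 30% are used, equal in both arms and at random. Early discontinuers are asked back for the Month 24 biopsy under a separate consent (Protocol 1.0), so dropout is not the same as missing. The Month 12–Month 24 correlation and the share of the effect visible at Month 12 are also assumed.

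**Step 1: the plan's own figures.** Enumerating Binomial(40, 0.30 + TE) against Binomial(20, 0.30) with no missing data reproduces all 21 cells of SAP Table 1 within 0.48 points. At TE 15 it gives 22.8/23.8/53.4% against the stated 23/24/53%. The match needs differences of exactly 5% or 15% to be sorted by ordinary floating-point comparison; with exact tie handling, no boundary convention comes closer than a largest gap of 6.2 points. Table 1 therefore describes complete data, not the imputed estimator.

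**Step 2: limiting case, Month 12 carries no arm information.** Let m be the missing fraction and p_E, p_P the true response rates. With 2:1 allocation, every missing subject is imputed at the pooled rate q = (2p_E + p_P)/3. Then:

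- emricasan estimate = (1 − m)p_E + m·q
- placebo estimate = (1 − m)p_P + m·q
- difference = (1 − m)(p_E − p_P)

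With p_E = 0.45, p_P = 0.30 and m = 0.20:

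- q = (0.90 + 0.30)/3 = 0.40
- emricasan = 0.8 × 0.45 + 0.2 × 0.40 = 0.44
- placebo = 0.8 × 0.30 + 0.2 × 0.40 = 0.32
- difference = 12 points, not 15

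At 10, 20 and 30% missing, a true 15 becomes 15 × 0.9 = 13.5, 15 × 0.8 = 12.0 and 15 × 0.7 = 10.5. At 20% missing the true difference must be 15/0.8 = 18.75 for the estimate to average 15. A true 0 stays 0.

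**Step 3: Month 12 always observed and already showing the full effect.** Large-sample simulation (latent bivariate-normal scores cut into ordered levels), true difference 15:

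| Correlation | 10% missing | 20% missing | 30% missing |
|---|---|---|---|
| 0.5 | 14.2 | 13.5 | 12.7 |
| 0.7 | 14.5 | 14.0 | 13.5 |
| 0.9 | 14.8 | 14.6 | 14.4 |

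A placebo rate of 70% gives nearly the same values. A separate simulation on Ishak scores, using the SAP's two predictor lists, shrank more. With 20% missing, Month 12 observed and a true difference of about 16, omitting arm gave 12.8 to 13.9 points (14–19% shrinkage). Including arm left about 2–3%.

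**Step 4: trial size.** 6,000 trials of 40/20, placebo 30%, correlation 0.7, 20 imputations. Ranges run from Month 12 always observed with full effect to Month 12 carrying no effect and missing whenever Month 24 is. With no missing data, P(estimate ≥ 15%) is 52–54% at a true 15 and 68–69% at a true 20, in line with Table 1.

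| True difference | Missing | P(estimate ≥ 15%), arm omitted | P(estimate ≥ 15%), arm included |
|---|---|---|---|
| 15 | 10% | 45–49% | 50–51% |
| 15 | 20% | 40–47% | 50–51% |
| 15 | 30% | 34–44% | 49–50% |
| 20 | 10% | 60–65% | 65–66% |
| 20 | 20% | 53–62% | 63–65% |
| 20 | 30% | 47–60% | 63–64% |
| 0 | 10–30% | 8–11% | 11–13% |

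Mean estimates at a true 15, for 10/20/30% missing:

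- without arm: 13.2–14.6 / 11.8–13.7 / 10.3–13.3
- with arm: 14.5–15.1 / 14.6–14.9 / 14.3–14.6
- observed cases only: 14.7–15.2 throughout

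**Step 5: scale.** SE = √(0.45 × 0.55/40 + 0.30 × 0.70/20) = √0.0167 ≈ 13 points. The shift at a true 15 runs from 15 − 14.6 = 0.4 to 15 − 10.3 = 4.7 points.

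**The case against.** The strongest reply is that the bias is one-directional only if missing subjects carry the full drug effect. Those who decline to return for a biopsy may well be off drug. In a simulation with 20% missing and no remaining effect in those subjects, the true intention-to-treat difference was 12.1. The SAP model gave 12.1 and adding arm gave 14.5. With half the effect remaining (true 13.7) the two gave 12.4 and 14.6. This stands: the direction holds under missing at random within arm, not in general. It does not justify the text as written. The SAP states no such assumption, and the arm-free model also raises the placebo rate (0.32 rather than 0.30 in Step 2).

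Second, omitting arm lowers total error: root mean squared error was 11.3–12.8 points without arm and 12.7–14.4 with it. That is true, but it is undeclared shrinkage whose size depends on how many biopsies are missing.

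Third, SAP 4 says the categories are not strict rules, and the middle one can still lead to Phase 3. The chance of falling below 5% at a true 15, even in the limiting case, rises only to 24/27/30% from 23/25/26% with arm. This limits the consequence.

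Fourth, part of the shortfall against Table 1 comes from missing data itself: with arm included, P(estimate ≥ 15%) at a true 20 is still 63–66% against the stated 68%. Only the gap between the last two columns in Step 4 belongs to the omission.

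Finally, the planned observed-case analyses avoid the problem, but they are sensitivity analyses.

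**Conclusion.** The concern holds. As written, both imputation models exclude arm, and the imputed estimate is the one read against the guideline. Under missing at random within arm and a real effect, the estimate is diluted by at most about the missing fraction, and by less where Month 12 is observed and informative. At a true 20 points, leaving out arm costs between about 1 and 17 percentage points in the chance of reaching 15%, depending on the assumed missing rate (10–30%) and on what Month 12 carries. With no true effect there is no bias and false positives do not rise. The omission is certain from the text; its size is not, because the documents give no missing rate. It should be corrected, but it is modest beside the trial's sampling error.

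**What to change.** In SAP 9.1, add randomised treatment group as a covariate to the predictors of both the Month 24 and the Month 12 imputation models, and say how a subject missing both biopsies is imputed. If imputation by arm was always intended, the section should say so. A covariate is preferable to separate imputation within arm because the placebo arm has only 20 subjects.

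The change is one term in two sentences and in the code, made before database lock; arm is known for every randomised subject. There are three costs:

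- The SD of the estimate at a true 15 rises to 13.0–13.9 points, from 10.9–12.5.
- With no true effect, the chance of an estimate of at least 15% is 11–13% rather than 8–11% (Table 1: 11%).
- The model relies on missing at random within arm, which could credit subjects who stopped treatment with full drug effect.

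The planned analysis counting missing Month 24 biopsies as non-response helps to check the last point, though it tests a different assumption. If the sponsor prefers a conservative primary estimate, that assumption should be declared.

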9.2 SECONDARY EFFICACY ANALYSES

All secondary analyses will be conducted using the FAS. All secondary endpoints based on the Months 12 and 24 liver biopsies will include data as collected (per [Section 3.5](#)). All secondary endpoints will be summarized using observed cases.

No multiplicity adjustments will be made for the analysis of secondary endpoints.

9.2.1 Secondary Efficacy Analysis: Testing the Difference in Response Rates Stratified by Baseline Ishak Fibrosis Score

Testing of differences in response rates will be conducted using a Cochran-Mantel-Haenszel test. For each of the analyses described in [Section 9.1](#) above, the testing will be stratified separately by each of the following:

- Baseline Ishak fibrosis score strata (F2, F3-F5, F6)
- Baseline Ishak fibrosis score grouping A (F2-F3, F4-F6)
- Baseline Ishak fibrosis score (F2-F6)

9.2.2 Secondary Efficacy Analysis: Change from Baseline in Ishak Fibrosis Score

Changes from baseline for the Ishak fibrosis score will also be summarized descriptively by treatment group using a shift table.

